6.2 Informed Consent

People who express interest in taking part in the study, and whose expression-of-interest (EOI) form suggests they are eligible will be telephoned to confirm eligibility and ensure they understand the required commitment if they decide to proceed. Those who are still interested will be emailed a link to the participant information and consent form (PICF). They will be able to download a PDF of the PICF, and a copy of their completed questionnaire will be emailed to them and the Sun-D email account.

The PICF will describe the purpose of the study, the procedures to be followed, and the risks and benefits of participation. A helpline will be available for potential participants who have additional questions. Participants will be asked to consent online, after which they will be asked to complete the baseline questionnaire online. When consent and questionnaire are complete, participants will be provided with either online (printable) or hard copy pathology collection form. When the blood sample is received, the participant will be randomised and the study intervention will begin.

6.3 Inclusion Criteria

In order to be eligible to participate in this study, an individual must meet all of the following criteria:

- Provide electronic consent to participate
- Willing to comply with all study procedures and be available for the duration of the study
- Aged 18 to 70
- Resident of Queensland, New South Wales, Victoria or Tasmania
- Fitzpatrick skin type 1 to 4

Women of reproductive potential may be recruited. There are no specific contraceptive requirements.

6.4 Exclusion Criteria

People will be excluded if they are unable to provide consent or unable to communicate well enough in English to understand study requirements. In addition, they will be excluded if they:

- Have a history of allergic skin reaction to sunscreen
- Have an autoimmune condition that affects the skin, such as psoriasis, lupus of the skin, scleroderma
- Have a history of melanoma within the past 5 years
- Are currently using sunscreen on a regular basis (i.e., > 2 days per week), excluding makeup or moisturiser with max SPF 15+ on the face
- Are taking or plan to start taking > 400 IU/day of supplementary vitamin D
- Do not have a phone

• Do not have access to electronic device suitable for survey completion and receiving reminders.

7 Study Intervention

7.1 Intervention Assignment / Randomisation Procedures

Participants will be randomised into one of the two groups, (the sunscreen intervention or control group), using permuted block randomisation within strata defined according to state of residence (QLD, NSW/ACT, VIC, TAS), age (18-44, 45-70), and sex (M, F). Study staff and investigators will be blinded to the allocation sequence. Once all baseline components are returned the database will automatically apply the next record in the allocation sequence (within the relevant stratum).

7.2 Blinding Procedures and Code Break

As it would be unethical to provide placebo sunscreen products, the study will be an open-label RCT. Therefore, following randomisation, participants and study staff will be aware of group assignment. However, analysts and laboratory staff will be blinded to group assignment. This will be achieved in two ways:

Analysts - A researcher external to the study team will generate preliminary datasets containing replacement identification numbers and new assignment codes which have no relationship to the original assignment. Once statistical code has been finalised the external researcher will execute the programs to produce results for the actual randomisation allocation.

Laboratory staff – Laboratory staff will not have access to the dataset containing participant allocation codes, and samples will be labelled with the participant identifier only.

7.3 Study Intervention Description

Both groups will be directed to the Cancer Council sun protection information at the start of the study. The control group will receive no further intervention.

Participants in the intervention group will be supplied with Hamilton Active Family SPF 50+ (500 mL) and instructed to apply a generous even layer to all skin not covered by clothing every day when the maximum UVI is forecast to be ≥ 3 . A separate facial sunscreen will be offered and supplied if preferred; Hamilton Everyday Face SPF 50+ (75gm). Hamilton Sensitive will also be available and provided on request to participants who are not able to tolerate Hamilton Active Family and/or Hamilton Everyday Face sunscreens.

Hamilton Active Family:

Active ingredients: Octyl Salicylate 5%, Homosalate 10%, Butyl Methoxydibenzoylmethane 4%, Octocrylene 8%.

Preservatives: Phenoxyethanol, Benzyl Alcohol, Hydroxybenzoates

Hamilton Everyday Face:

Active ingredients: Octocrylene 3%, Butyl Methoxydibenzoylmethane 3%, 4-Methylbenzylidene Camphor 2%, Ethylhexyl Triazone 2% Preservatives: Phenoxyethanol Hamilton Sensitive:

Active ingredients: 4-Methylbenzylidene Camphor 4%, Butyl Methoxydibenzoylmethane 4%, Octocrylene 4%, Ethylhexyl Triazone 3% Preservatives: Caprylyl glycol, octanohydroxamic acid, glycerol

Sunscreen will be mailed to participants at the beginning of the trial. Replacements will be sent as requested. All product will be labelled as follows:

SUN-D STUDY SUNSCREEN For participant use only Participant ID: _______ Participant Name: _______ Directions for use: Apply liberally to exposed skin, when the maximum UV index is forecast to reach 3. PLEASE RETAIN PACK FOR RETURN TO SUN-D TRIAL Phone contact 1300 XXX XXX Dispensed on: dd/mm/yyyy Item number: PXX EXP:mm/yyyy P3755 [name] - QIMR Berghofer Medical Research Institute, [name]

Note: Study labels will be fixed to the front of the product leaving the storage advice, ingredients list, and other important product information visible on the back of the pack.

7.4 Storage and Handling

The IP will be held at room temperature in a secure QIMR Berghofer facility that has temperature logging enabled. Any temperature deviations above 30 degrees Celsius will be recorded, although short elevations will have minimal impact on the sunscreen product.

Participants will be instructed to store sunscreen in a cool place (below 30° C) away from sunlight as per the manufacturer's instructions.

7.5 Dispensing and Accountability

Key Pharmaceuticals will provide Hamilton Active Family SPF 50+ (500 mL lotion in bottle with pump dispenser), Hamilton Everyday Face SPF 50+ (75 gm cream in tube) and Hamilton Sensitive (265 mL lotion in bottle) to QIMR Berghofer.

When a participant is randomised to the intervention group they will be dispensed an initial quantity of sunscreen suitable to their location (calculated based on the expected amount of sunscreen required for the following 6 months). All participants in the intervention group will be provided with 500 mL pump packs of general use sunscreen. Those who wish to use it will also be provided with facial sunscreen.

A letter and product labels will be printed, identifying the participant and providing instructions for storage, use, and product return. Labels will be fixed to the front of each tube/bottle of sunscreen and packed together with the letter for posting. Address labels will be attached to each pack, and the contents of the pack will be checked against the dispense report to ensure the correct type and quantity of sunscreen has been dispensed.

At the time of each monthly survey, participants will be asked to indicate if they need replacement sunscreen, and the type required (general and/or face). These will be dispensed as above.

Participants will be provided with a return satchel, and asked to store all empty bottles/tubes in the satchel for return at the conclusion of the study.

The Sun-D database will keep an up to date log of sunscreen supplies (type, quantity, dispense date, item number and batch information) dispensed to participants. Sunscreen bottles returned will be logged, along with the weight of each bottle. Quantities for each dispensed bottle will be updated in each tri-monthly participant interview and finalised at the conclusion of the intervention.

Note: we will offer additional sunscreen to families to minimise use of study sunscreen by other family members. It will be labelled as family use sunscreen. Sunscreen sent to families will also be captured in the Sun-D database.

7.6 Intervention Administration and Dose justification.

Following randomisation the control group will be instructed to maintain their usual sunscreen routine.

Participants in the intervention group will be instructed to apply the provided sunscreen liberally to all skin not covered by clothing every day when the maximum UVI is forecast to reach 3. The intervention is based on current recommendations for sunscreen use, for people living in Australian and New Zealanders,³¹ and aims to assess the impact of this advice on 25(OH)D concentration at the end of summer and winter.

The intervention will last 1 year. Within individuals, 25(OH)D concentration is relatively stable from year to year but will fluctuate by season. The intervention period has been chosen to allow for this seasonal variation. A 1-year intervention will provide adequate data to answer the research question.

In line with the selection criteria (see 6.3-4) we will request participants limit supplementary vitamin D intake to 400 IU/day for the duration of the study. However, once randomised, participants will not be withdrawn for taking more than 400 IU/day. Vitamin D dose information will be captured in monthly surveys to assist in trial monitoring and for use in analyses at the conclusion of the study.

7.7 Intervention Dose Modifications

No dose modifications will be required. Participants who experience an adverse reaction (i.e., a skin rash) will be withdrawn if symptoms do not resolve and no other cause is identified.

NOTE: Participants withdrawing due to adverse reaction will be invited to continue monthly surveys and provide bloods in according to their planned schedule.

7.8 External monitoring

The investigational product is classified as a therapeutic sunscreen, and is therefore subject to additional regulatory requirements external to the trial. In light of this, it is possible that product quality, contamination and labelling issues may be revealed during the course of the trial. Should any issues become apparent, participants will be notified and advice provided in line with the TGA recommendations. Study staff will confirm advice is received and acted on appropriately by telephone and/or email contact with each individual.

7.9 Intervention / Treatment Compliance

We will use self-reported frequency from the monthly surveys as the primary measure of the number of days sunscreen was applied. Compliance will be calculated as the number of days applied divided by the number expected. Any Sunscreen bottles returned to QIMR B will be

weighed and their weights recorded in the Sun-D REDCap database. Participants will not be withdrawn for being non-compliant. However, compliance information will be routinely collected at each monthly survey. Participants reporting significant non-compliance will be contacted for further review in an effort to identify barriers and suggest solutions where possible. Compliance data will also be reviewed regularly by the Trial Management Group (TMG) – see section 11.2.2 and appendix 1.

We will update information on sunscreen supply during tri-monthly interviews with intervention group participants and again at the conclusion of the intervention period.

Note: The number of days expected will be estimated based on the number of days where the forecast maximum UVI at the closest town was ≥ 3 (using data from the Bureau of Meteorology).

7.10 Discontinuation of Intervention and Withdrawal of participants

7.10.1 Criteria for Discontinuation

Participants can withdraw from the study at any time by notifying us in writing, or via email or phone. Those in the sunscreen arm can discontinue using the study sunscreen at any time. They will be invited to continue surveys and blood collections as scheduled.

Participants who cease the monthly surveys will be invited to continue blood collections as scheduled.

Participants will be withdrawn from the study for any of the following reasons:

- Withdrawal of informed consent
- Experience an ongoing reaction to the sunscreen product (sunscreen group only)
- Death
- Discontinuation of the study by the Sponsor, a Regulatory Authority, or a Human Research Ethics Committee

7.10.2 Handling of Participant Discontinuation and Withdrawal

Participants do not have to give a reason for their withdrawal. Information already collected will be destroyed at their request.

The following information will be captured in the Sun-D Trial database for all participants who withdraw / are withdrawn from the study at the time of withdrawal:

- Date of withdrawal
- Reason for withdrawal: (including an option for no reason given)
- Willing to keep completing surveys: yes / no
- Willing to keep giving blood samples
- Willing for us to keep information already collected: yes / no (details if any caveats)
- Willing for us to obtain information in the future (MBS/PBS records): yes / no

No withdrawn participants will be replaced.

7.11 Premature Termination or Suspension of Study

The Sponsor, Principal Investigator(s), Human Research Ethics Committee (HREC) and Regulatory Authorities independently reserve the right to discontinue the study at any time for safety or other reasons. This will be done in consultation with the Sponsor where practical. In the occurrence of premature trial termination or suspension, the above mentioned parties will be notified in writing by the terminator/suspender stating the reasons for early termination or

suspension (with the exception of the sponsor's responsibility for notifying the Regulatory Authorities). After such a decision, the Sponsor and the Investigator will ensure that adequate consideration is given to the protection of the subjects' interests. The investigator must review all participating subjects as soon as practical and complete all required records.

8 Study Procedures and Assessments

	Study year		1	l	1			2				3			
	Calendar year		2021 202		22			2023			2024				
	Quarter	Q3	Q4	Q1	Q2	Q3	Q4	Q1	Q2	Q3	Q4	Q1	Q2		
Stage 1	Set-up														
ge 2	Participant recruitment (invitations sent, EOIs completed, screening calls conducted and baseline materials returned)														
Stage	Intervention and follow-up (Intervention, monthly surveys completed and blood samples returned)														
3	25(OH)D assays														
Stage	Data analysis and publication														
S	Stakeholder meeting														

8.1 Schedule of Assessments

Note: Year 1 begins on 1 July 2021; Participants will be involved only in stage 2, beginning with recruitment in the first half of 2022, just prior to the start of study year 2 and ending with the final blood collection in the third quarter of 2023. The intervention and follow-up are described in more detail below (section 8).

8.2 Study Assessments

8.2.1 Recruitment / Baseline

On receipt of completed eligibility questionnaire, potentially eligible people will be contacted by phone to confirm their eligibility information, as well as willingness and ability to adhere to study requirements. After phone contact, people who are eligible and willing to take part will be sent a link to online:

- Trial information sheet and consent form
- Baseline questionnaire

Participants who complete the consent and baseline questionnaire will then be able to access a pathology request form, and asked to provide a blood sample before the end of September 2022. Participants will be able to request a hard copy of the request form. Randomisation will take place once both consent and baseline questionnaire have been completed and checked, and the baseline blood sample has been received by sample processing at QIMR Berghofer.

8.2.2 Follow-up

Following randomisation participants in the intervention group will receive sunscreen supplies as described above (see section 7.5). They will also be provided with access to a short video clip showing optimal sunscreen application. In addition, the following reminders and support will be provided:

- Weekly reminders, including information about the forecast UVI
- Invitation to a closed Facebook group providing access to videos, hints about sunscreen application, sunscreen and sun exposure facts etc.
- Regular email updates about study progress, including short videos to encourage application
- Advice about how to download and use the SunSmart App which displays the daily forecast UVI for their location.
- After the first two weeks and then bi-monthly we will telephone participants in the intervention group to identify barriers to sunscreen use and to suggest solutions.

8.2.3 Surveys

Baseline questionnaire

The baseline questionnaire will capture information about: demographics; phenotype, including sun susceptibility; lifestyle; skin cancer history; sun exposure behaviour; use of supplementary vitamin D.

Follow-up surveys

Each month all participants will be asked to complete a short online survey which will capture information about: sunscreen use, time outdoors, clothing when outdoors, use of vitamin D supplements, adverse events.

Final Survey

At the end of the final month of participation, each participant will receive a final survey. This survey will include all questions asked in the monthly follow-up surveys, and in addition, will contain a short section capturing travel information, attitudes towards vitamin D, sun exposure, sunscreen, and participant feedback.

8.2.4 Blood collection

Three blood samples will be collected from eligible participants who have completed the consent form and baseline survey.

Sample 1

The baseline blood sample will be collected in winter to early spring: (Jun - Sept 2022). Eligible participants will be required to provide a baseline blood sample before the end of September in order for randomisation to take place.

Samples 2 and 3

The second and third samples will be collected at end of summer (Feb – March 2023), and at the end of the intervention phase (winter to early spring: Jul – Sept 2023).

Participants will be provided with either online (printable) or paper pathology collection forms to be presented at their local participating pathology laboratory. Blood samples will then be returned to QIMR Berghofer for processing and storage.

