4.2.2 Secondary Objectives

Secondary objectives are to:

- Determine whether the intervention affects 25(OH)D concentration at the end of winter or summer within tertiles of:
 - Erythemally weighted ambient UV radiation at the postcode of usual residence
 - Baseline 25(OH)D concentration
- Identify environmental and participant factors that influence the change in 25(OH)D concentration in sunscreen users.
- Identify barriers to knowledge and attitudes about sun protection, and facilitators and barriers to regular sunscreen use.
- Determine if randomisation to regular SPF 50+ sunscreen application reduces the incidence of malignant and pre-malignant skin lesions.

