10.3 Statistical Analysis Plan

Intention-to-treat analyses: Our main analyses will follow an intention-to-treat approach. 25(OH)D values in the Australian population are approximately normally distributed so we will model 25(OH)D as a continuous outcome using longitudinal analysis of covariance (ANCOVA). We will include treatment group (daily sunscreen or control), time, and the

interaction between treatment and time to estimate the difference in 25(OH)D concentration between treatment groups at the end of summer and at the end of winter. This method has been shown to reliably estimate the effect of treatment, accounting for any differences in the baseline value of the outcome measure.³³ All models will be adjusted for the variables used to stratify the randomisation and will include baseline 25(OH)D concentration as a covariate and participant as a random effect.

We will perform the analyses within the whole cohort and separately within tertiles defined according to: (1) average ambient UVR; and (2) baseline 25(OH)D concentration.

The incidence of skin lesions between the two groups will be assessed using Poisson regression.

Sensitivity analyses: To assess the effect of lack of compliance with the sunscreen intervention in the sunscreen group, and any routine sunscreen use in the control group, we will perform:

(a) An as-treated analysis using propensity score adjustment to minimise confounding. We will categorise sunscreen use into low (<30% of eligible days), moderate (30 to <70%), and high (\geq 70%). A generalised boosted model will be used to estimate the propensity score for sunscreen use, from which we will derive inverse probability of treatment weights. These will be used as weights in the ANCOVA models, both overall and within strata.

(b) Instrumental variable principal stratification to estimate the complier average causal effect, using the randomised allocation as the instrumental variable.³⁴ This method preserves the randomisation

Those in the intervention group will be classified as compliant if they used sunscreen on at least 70% of eligible days, and those in the control group will be classified as compliant if they used sunscreen on fewer than 20% of eligible days.

11 Responsibilities

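### Blood is drawn over windows of two to four months, yet section 10.3 names no draw-date term and cuts the baseline tertiles on 25(OH)D as measured (minor)

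*Protocol*

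**What the plan says.** **Sampling windows (Protocol 8.2.4, repeated in 9.6).** For sample 1: "The baseline blood sample will be collected in winter to early spring: (Jun - Sept 2022"). For the other two: "The second and third samples will be collected at end of summer (Feb – March 2023), and at the end of the intervention phase", the last of these running over July to September 2023.

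**Model (10.3).** The protocol writes "We will include treatment group (daily sunscreen or control), time, and the" interaction between them. Time here means the sampling occasion, end of summer or end of winter. It continues: "All models will be adjusted for the variables used to stratify the randomisation and will include baseline 25(OH)D concentration as a covariate", plus a participant random effect. No draw date, month or day of year is named.

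**Tertiles (4.2.2 and 10.3).** Analyses are repeated "separately within tertiles defined according to: (1) average ambient UVR; and (2) baseline 25(OH)D concentration". No date adjustment of the baseline value is mentioned.

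**Seasonality.** Section 7.6 says that 25(OH)D fluctuates by season within individuals. Section 2.1 puts the share below 50 nmol/L at 36% in winter, 14% in summer and 23% overall. No month-by-month curve and no date for the annual low point is given anywhere.

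**Order of events (6.2, 8.2.1).** Randomisation follows receipt of the baseline sample.

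**The concern.** A value drawn in early June and one drawn in late September count as the same baseline measurement. If 25(OH)D moves across that window, part of the difference between two participants is the calendar and not their vitamin D status.

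The tertiles are where this matters most. Section 10.1 finds 115 per group and then multiplies by three, because fully powered analyses within tertiles are wanted to support public health and clinical messages. Hypothesis 2 in section 2.2 also concerns every stratum. A tertile labelled as low baseline that is partly a draw-month group blurs whom the message is for.

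A smaller issue is precision: unmodelled drift at baseline and at follow-up adds residual variance to the primary model. A third, conditional issue is that samples 2 and 3 are drawn after open-label randomisation. If draw dates within a window differed between arms, seasonal drift would enter the contrast.

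**Working it through.** **1. The plan's own sample size.** Inputs from section 10.1: SD 20, correlation 0.6, difference 10 nmol/L, one-tailed 5%, power 90%, 20% non-compliance, 10% uptake in controls, 20% loss.

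- Residual SD = 20 × √(1 − 0.6²) = 16.
- Diluted effect = 10 × (1 − 0.20 − 0.10) = 7.
- n = 2 × [16 × (1.645 + 1.282) / 7]² = 89.5, so 90 per group; 90 / 0.8 = 112.5, so 113.

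The stated 115 is reproduced to within 3%. Completers per group per tertile: 115 × 0.8 = 92.

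**2. Size of the seasonal swing.** From section 2.1, assuming normality with SD 20:

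- Winter mean = 50 + 20 × 0.358 = 57.2.
- Summer mean = 50 + 20 × 1.080 = 71.6.
- Gap = 14.4 nmol/L.

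**3. Assumed curve.** f(t) = −A cos[2π(t − trough)/365]. A three-month average of a cosine centred on its trough keeps a fraction 0.900 of the amplitude, and a trough later than mid-July adds a factor cos(30° × months of delay). So A = 14.4 / (2 × 0.900 × cos(lag)). The trough date is not in the documents and is varied.

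**4. Simulation.** Baseline draws even over June to September, final draws even over July to September, r = 0.6, SD 20. A changed tertile means a different tertile from the one assigned after removing f(t). The residual-variance column is the cut achieved by adding date terms.

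| Assumed trough | A (nmol/L) | June minus September mean | Changed tertile | Lowest-tertile share, June / September draws | Cut in residual variance |
|---|---|---|---|---|---|
| Mid-July | 8.0 | about −3 | 5% | 34% / 29% | 2% |
| End July | 8.3 | about 0 | 4% | 32% / 31% | 1% |
| Mid-August | 9.3 | about +3 | 5% | 29% / 34% | 1% |
| End August | 11.3 | about +8 | 10–11% | 24% / 38% | 2–3% |
| Mid-September | 16.0 | about +16 | 19–20% | 17–18% / 45% | 9–10% |

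The ranges in the last two rows reflect small differences in how the amplitude is matched. Of 690 participants, 4% to 20% is 28 to 138 people. The moves are across one cut-point; essentially nobody moves two tertiles. With an end-August trough, about 92% of the lowest tertile would still be there after date adjustment.

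**5. Precision and power by a separate route.** Assume instead a linear fall of 5, 10 or 15 nmol/L over the window, added on top of r = 0.6 and SD 20 at baseline and, scaled to three months, at follow-up. The standard error of the treatment effect rises by 0.4%, 1.5% or 3.3%. Power per tertile with 92 completers per group goes from 90.7% to 90.5%, 90.0% or 89.0%. Whole-cohort power with 276 per group stays above 99.9%.

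**6. Follow-up timing, conditional only.** If one arm's final draws centred on 8 July and the other's on 22 July, the curves above would shift the winter contrast by 0 nmol/L (mid-July trough) to about 3.4 nmol/L (mid-September trough). For scale, section 10.1 quotes a non-inferiority margin of 4.5 nmol/L.

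**The case against.** The strongest reply is that a day-of-year covariate or a date-standardised cut-point is ordinary SAP detail, and that silence in section 10.3 does not exclude it. That is fair as far as it goes: the protocol does not rule draw date out, and a separate SAP may include it. But section 10.3 is itself headed as the statistical analysis plan, lists the covariates for all models, and defines the tertiles on baseline 25(OH)D. The point is therefore an improvement to a stated specification.

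Three stronger readings are tempting and are not supported.

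- **That 25(OH)D falls throughout the baseline window, so that late drawers crowd the lowest tertile.** No section says so. With a mid-July trough the direction reverses, and with an end-July trough early and late draws nearly cancel. The late troughs that give the largest figures also fit section 2.1 least well: the same curve implies about 24.4% of people below 50 nmol/L over the year for a mid-July trough, 25.2% for end August and 26.7% for mid-September, against the stated 23%.
- **That the treatment comparison is biased.** Baseline draw date, and hence tertile, is fixed before randomisation, so neither can bias the contrast overall or within tertiles. Follow-up dates could differ by arm in an open-label trial, but nothing shows that they do. Both arms get the same pathology forms, the same voucher per sample and the same monthly surveys. The extra intervention contact described in sections 6.1 and 8.2.2 is mainly about sunscreen use.
- **That the primary analysis loses meaningful power.** It does not (step 5). Moreover, the planning correlation and SD come from a cohort measured in all four seasons, so some seasonal noise may already be in them.

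**Conclusion.** The point holds as a minor one. As specified, the baseline tertiles mix vitamin D status with date of draw to a degree that the documents do not allow one to fix. About 4% to 20% of participants would be assigned differently after date adjustment, with 4% to 5% for troughs from mid-July to mid-August. The gain in residual variance is 1% to 2% for most troughs and about 9% at the extreme. These figures rest on a sinusoidal curve matched to the winter and summer prevalences, SD 20, evenly spread draws and an assumed trough between mid-July and mid-September.

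The randomised comparison remains valid overall and within raw tertiles. What is weakened is the meaning of a tertile, and that matters somewhat because the tertile analyses set the total of 690 and are meant to carry the messages. A reader might infer that baseline-specific messages would be given to the wrong people; overlap of about 92% in the lowest tertile with an end-August trough (about 86% with mid-September) does not bear that out.

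**What to change.** Keep all sampling windows. In section 10.3:

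1. Add draw date to the longitudinal ANCOVA as a harmonic day-of-year term, for the baseline sample and for the follow-up samples.
2. Form the baseline tertiles on 25(OH)D standardised to a common calendar date, using a seasonal term fitted to the baseline samples without reference to arm. Keep the raw tertiles as a sensitivity analysis.
3. Report the distribution of draw dates by arm at each of the three samples. This settles whether follow-up timing differs.

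No extra visits or samples are needed. The change assumes that collection dates are held in the trial database; section 11.2.5 lists blood sampling among the items captured. Because section 8.2.6 defers all assays to the end of the study, it can be specified before any 25(OH)D result is known. The costs are a few extra parameters and reliance on a fitted seasonal term, which is why the raw tertiles should still be reported.
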